### 5.6.4.2 Handling of Missing Data

Little missing data is expected for this endpoint. If there is missing endpoint data, a multiple imputation approach will be used based on a fully conditional specification. The imputation model will include the following covariates: age, sex, and baseline CNC. An augmented likelihood approach will be used if need to facilitate modeling. A total of 100 imputed data sets will be generated and results combined for inferential purposes.

Statistical Analysis Plan		Page 11 of 13	
Sponsor	Study		Version
Cochlear Americas	A pivotal, prospective, multi-center, open- label study evaluating the safety and effectiveness of the Cochlear ™ Osia ® 2 System in a pediatric population		1.0

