### 6.2.6 Criteria and Procedures for Subject Withdrawal

Subjects can decide to withdraw from the investigation at any time. The Investigator shall ask the reason(s); however, subjects have the right to withhold their reason if preferred. The reason for withdrawal should be documented in the subject's source files and the case report form (CRF), if provided.

The Investigator or Sponsor may also decide to withdraw a subject from the clinical investigation or stop the use of the investigational device if it is considered to be in the subject's best interests.

Subject withdrawal may be for any of the following reasons:

- Adverse Event (AE)
- Device Deficiency (DD)
- CIP or GCP deviation
- Subject withdrew consent
- Subject lost to follow-up
- Subject death
- Sponsor decision
- Investigator decision
- Other (specify)

If subject withdrawal is due to problems related to the safety or performance of the Osia 2 system, the Investigator may ask for the subject's permission to continue in safety follow up (for example, adverse events and device deficiencies) until their scheduled End-of-Study visit at Visit 5.

If a subject is lost to follow-up, every possible effort must be made by the study site personnel to contact the subject and determine the reason for discontinuation. At least 3 separate attempts taken to contact the subject must be documented.

Participating subjects who are withdrawn/discontinued will not be replaced.

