### 6.3.2.2 Description of Speech Perception Testing

### 6.3.2.2.1 Consonant Nucleus Consonant (CNC) Monosyllabic Words

The CNC Word Test (Peterson & Lehiste, 1962) consists of 10 recorded lists of 50 monosyllabic words. For this study, one list will be administered per test condition at 60 dBA at 0° azimuth (S0) in sound field and scored as the number of phonemes and words correct, which will be expressed as a percentage correct when analyzed. Preoperatively, CNC Words will be assessed in the unaided condition as well as the aided condition using the Baha 5 Power on a softband. Postoperatively, CNC Words will be assessed only in the aided condition using the Osia 2 sound processor. Pre and postoperative testing will be completed with the contralateral ear plugged or muffed in an effort to isolate the treated ear.

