### 4 Sample Size Determination

Sample size for the study is not driven by power requirements for a formal statistical hypothesis test. The planned sample size of 50 subjects will provide data to characterize safety and effectiveness with a reasonable degree of statistical precision. Additionally, the planned sample size will allow for a high probability of observing events of interest. For example, with 50 subjects, the half-width of a two-sided 95% confidence interval for a continuous endpoint based on a t-distribution would be 0.284 units on the effect size scale. Similarly, with 50 subjects, there is a greater than 95% probability of observing one or more events that occur at a population rate of 5.9%

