#### 5.6.2.2 Handling of Missing Data

Little missing data is expected for this endpoint. If there is missing endpoint data, a multiple imputation approach will be used based on a fully conditional specification. The imputation model will include the following covariates: age, sex, and baseline SSQ. An augmented likelihood approach will be used if need

St	atistical Analysis Plan	Pa	ge 9 of 13
Sponsor	Study		Version
Cochlear Americas	A pivotal, prospective, multi-center, open- label study evaluating the safety and effectiveness of the Cochlear ™ Osia ® 2 System in a pediatric population		1.0

to facilitate modeling. A total of 100 imputed data sets will be generated and results combined for inferential purposes.

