#### 5.6.4 Secondary Endpoint 3 – CNC Words

Secondary endpoint 3 is defined as the mean difference between baseline unaided speech perception in quiet and the aided condition using the Osia 2 system at 6 months post-surgery on open-set monosyllabic word recognition (CNC Words) in quiet.

### 5.6.4.1 Primary Analysis of Secondary Endpoint 3

The secondary endpoint 3 will be assessed with the following hypothesis:

 $H_0$ :  $\Delta \leq 0$ 

 $H_a$ :  $\Delta > 0$ 

where  $\Delta$  represents difference between baseline unaided speech perception CNC and 6 months-post surgery CNC, specifically  $\Delta$  =  $CNC_{6\,Months}$  –  $CNC_{preop}$ . This difference is parameterized so that a positive value is indicative of a clinical improvement.

The hypothesis will be evaluated using a one-sample, one-sided 0.025 alpha level t-test for a mean against the null of zero. The objective will be met if the null hypothesis is successfully rejected.

The endpoint will be presented with descriptive statistics and the corresponding two-sided 95% confidence interval based on the t-distribution.

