#### 5.6.4.3 Sensitivity Analysis

In the event there is significant evidence of a departure from normality based on a Shapiro-Wilk test at the 0.05 alpha level, a Sign test (a non-parametric alternative) will be employed.

A tipping point analysis for missing data will be performed as a sensitivity analysis. This will impute values for the missing endpoint data, using all possible combinations of the "best" and "worst" observed results for the endpoint (i.e. all missing imputed as "worst", all missing imputed as "best", and all combinations between these extremes).

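### A 6-month score missing because the implant was removed or its link is unusable is imputed as if the device were working

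*SAP*

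**What the plan says.** - **Missing data.** SAP 5.6.4.2 states: "If there is missing endpoint data, a multiple imputation approach will be used based on a fully conditional specification". SAP 5.6.2.2 and 5.6.5.2 repeat the rule. The covariates are age, sex and the endpoint's own baseline; for the questionnaire, "The imputation model will include the following covariates: age, sex, and baseline SSQ". The list has no device status, device use, 3-month score or reason for missingness.
- **How the 6-month scores arise.** Protocol 6.3.2.2.1: "Postoperatively, CNC Words will be assessed only in the aided condition using the Osia 2 sound processor". Protocol 6.3.2.2.2 says the same of BKB-SIN, and Protocol 6.3.4.7 has the parent rate everyday listening with the Osia 2 on.
- **Who is analysed.** Protocol 8.5 and SAP 5.2 take children in whom implantation succeeded. Neither says what happens to a child whose implant is later removed. Discontinued children are not replaced (Protocol 6.2.6).
- **Follow-up after a device problem.** If withdrawal follows a safety or performance problem, Protocol 6.2.6 provides that "the Investigator may ask for the subject's permission to continue in safety follow up (for example, adverse events and device deficiencies"). It does not mention effectiveness data.
- **Sensitivity.** SAP 5.6.2.3, 5.6.4.3 and 5.6.5.3 add a tipping-point analysis "using all possible combinations of the 'best' and 'worst' observed results for the endpoint".
- **Test.** "The hypothesis will be evaluated using a one-sample, one-sided 0.025 alpha level t-test for a mean against the null of zero".

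**The concern.** Protocol 7.2.2 lists failure to anchor, extrusion and removal surgery as risks, and Section 16 names explant and discontinued use, so removal is a foreseen event. A child without a functioning implant at Visit 4 cannot produce an Osia-aided score. The imputation model has seen only children who could, and nothing in it tells the two apart. Its draws answer what the child would have scored with a working device, when the reason for the missing score is that there was none.

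The study has one arm and is meant to support a wider indication. SAP Section 4 says: "Sample size for the study is not driven by power requirements for a formal statistical hypothesis test". It justifies the sample by precision instead, so the mean gain and its interval are the main effectiveness result. An error in that mean that favours the device is worth removing even when it is small.

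**Working it through.** **Inputs.** N = 50 ("The planned sample size of 50 subjects will provide data to characterize safety and effectiveness", SAP 4). One removal among 51 implanted adults (Protocol 3.2.2.1). Mean gains of 79.1 points on PBK words and 2.10 on the SSQ-12 Parent in the earlier paediatric study (Protocol 3.2.2.2). The documents give no SD for any endpoint and no expected number of device failures.

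**The plan's own figures.** The half-width t(0.975, 49)/√50 is 0.2842, against 0.284 stated. The chance of at least one event at a 5.9% rate is 1 − 0.941^50 = 0.952, against more than 95% stated. Both reproduce, and neither is in dispute.

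**What the rule does in expectation.** Imputation was simulated with a normal model on age, sex and baseline, 100 imputations, Rubin's rules and 2,000 trials per scenario. The change SD was assumed to be 1, with k children missing. The mean imputed change for those children was:
- true users' effect 0.5 SD: 0.493, 0.508 and 0.495 for k = 1, 3 and 6;
- true users' effect 1.0 SD: 0.994, 0.995 and 0.999.

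The missing children receive the users' mean gain. Single draws vary.

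**Size.** With users' mean gain g, imputation gives about g. Scoring k failures as zero change gives g(50 − k)/50. The overstatement is g·k/50.

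| k | Zero-change mean ÷ imputed mean | Words, g = 79.1 | SSQ, g = 2.10 |
|---|---|---|---|
| 1 | 0.98 | 77.5 (over by 1.6) | 2.06 (over by 0.04) |
| 3 | 0.94 | 74.4 (over by 4.7) | 1.97 (over by 0.13) |
| 6 | 0.88 | 69.6 (over by 9.5) | 1.85 (over by 0.25) |

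**Which k is supported.** 50 × 1/51 = 0.98, so about one child. The chance of at least one is 1 − (50/51)^50 = 0.63. The rows for 3 and 6 are stress cases.

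**Test decision.** The smallest users' effect that reaches significance is 0.2872 SD on completers alone (close to the imputed analysis) and 0.2873 SD with zero change for k = 1. For k = 6 it is 0.3040 and 0.3042. At a true effect of 0.4 SD with k = 6, rejection was 71% imputed and 73% with zero change. The zeros lower the mean but also the spread.

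**Does the tipping-point analysis cover it?** Its floor is the worst observed result. At an effect of 0.5 SD and k = 6, the all-worst mean was 0.24 against 0.44 for zero change, so it was harsher. At 2.0 SD the worst observed change averaged about −0.2 SD, which is about 2.2 SD below the mean. Above an effect of about 2.2 SD the worst observed change is expected to be a gain, and the range no longer reaches zero benefit. For a 79.1-point gain this happens if the SD is below 79.1/2.2 = 36 points.

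**The case against.** The strongest reply is that Protocol 8.2.2.3 and 8.2.2.4 define the speech endpoints as performance with the Osia 2, so a device-on estimate is what was asked for. This stands in part. A device-on mean is a legitimate quantity, but neither document declares it as the target or says how removal enters it. Reporting both results answers the point.

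Failures are also visible elsewhere. Adverse events are the primary endpoint, early exits are tabulated by reason (SAP 5.4), events leading to discontinuation are listed (SAP 5.8), and evaluable counts are shown (SAP 5.3). That is correct. It limits the harm but leaves the mean gain unchanged.

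The size is modest. The planned half-width is 0.284 × SD: 5.7 points at an assumed SD of 20 and 10.2 at 36. An error of 1.6 points lies well inside either. The gains are borrowed: PBK is not CNC, and those children were aged 10 to 17 with no single-sided deafness. There is no corresponding figure for BKB-SIN.

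Three stronger readings are tempting, and the documents do not support them:
- A reader might infer that every child who stops wearing the processor is imputed as a user. The rule applies only to missing values. A child who has stopped daily use but is tested at Visit 4 has an observed score.
- A reader might take the one child in 14 whose thick skin flap blocked the link as a failure rate and expect 50/14 = 3.6 such children. Protocol 3.2.2.2 says that revision resolved the event and the child completed the study, so it is not evidence of a missing 6-month score.
- A reader might assume that the tipping-point analysis never reaches failure. At modest effects it goes beyond zero change.

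**Conclusion.** The concern holds in a limited form. For a child with no Visit 4 score because of an explant or unusable link not corrected by then, the main analysis of endpoints 1, 3 and 4 credits the users' gain in expectation, given age, sex and baseline. Relative to zero change, the mean is overstated by k/50, or about 2% for the one removal that the cited adult rate implies. That rate comes from adults, and the removal is not dated relative to 6 months. The 1.6 points and 0.04 are illustrations only.

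The documents do not support reading this as a threat to the hypothesis tests. Whether the tipping-point range reaches zero benefit depends on an SD that they do not give, and it remains a sensitivity analysis that treats an explant like a missed visit. The result assumes that explanted children stay in the analysis set. If successful implantation were read to exclude them, they would be dropped and the mean would again be that of users only. Endpoint 2, unaided bone conduction at 4 weeks, is not part of this point.

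**What to change.** In SAP 5.6.2.2, 5.6.4.2 and 5.6.5.2:
- limit multiple imputation to scores missing for reasons unrelated to the device, or for unknown reasons. A default for unknown reasons is needed because families may withhold the reason (Protocol 6.2.6);
- where the score is missing because of explant or an unusable link, set change to zero in the main analysis. The CNC and BKB-SIN baselines are unaided, which is roughly the state such a child returns to;
- report the number of such children, and keep the all-imputed result as a supplementary device-on estimate.

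In SAP 5.2, state that explanted children remain in the analysis set. In SAP 5.6.2.3, 5.6.4.3 and 5.6.5.3, extend the tipping-point range to include zero change. In Protocol 6.2.6, where the family agrees, collect the Visit 4 parent SSQ on actual everyday listening, and use that value for endpoint 1.

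The cost is a few sentences in the SAP and one in the protocol. Withdrawal reasons, where given, and device exposure are already recorded. The downsides are a slightly smaller reported mean gain and the need to classify why each score is missing.

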#### 5.6.4.3 Sensitivity Analysis

In the event there is significant evidence of a departure from normality based on a Shapiro-Wilk test at the 0.05 alpha level, a Sign test (a non-parametric alternative) will be employed.

A tipping point analysis for missing data will be performed as a sensitivity analysis. This will impute values for the missing endpoint data, using all possible combinations of the "best" and "worst" observed results for the endpoint (i.e. all missing imputed as "worst", all missing imputed as "best", and all combinations between these extremes).

#### 5.6.5 Secondary Endpoint 4 – BKB SIN

Secondary endpoint 4 is defined as the mean difference between baseline unaided speech perception in quiet and the aided condition using the Osia 2 system at 6 months post-surgery on an adaptive speech in noise test BKB SIN.

### 5.6.5.1 Primary Analysis of Secondary Endpoint 4

The secondary endpoint 4 will be assessed with the following hypothesis:

 $H_0$ :  $\Delta \leq 0$ 

 $H_a$ :  $\Delta > 0$ 

where  $\Delta$  represents difference between baseline unaided speech perception BKB SIN test and 6 monthspost surgery BKB SIN test, specifically  $\Delta = BKB_{6 \, Months} - BKB_{preop}$ . This difference is parameterized so that a positive value is indicative of a clinical improvement.

The hypothesis will be evaluated using a one-sample, one-sided 0.025 alpha level t-test for a mean against the null of zero. The objective will be met if the null hypothesis is successfully rejected.

The endpoint will be presented with descriptive statistics and the corresponding two-sided 95% confidence interval based on the t-distribution.

### 5.6.5.2 Handling of Missing Data

Little missing data is expected for this endpoint. If there is missing endpoint data, a multiple imputation approach will be used based on a fully conditional specification. The imputation model will include the following covariates: age, sex, and baseline BKB SIN. An augmented likelihood approach will be used if need to facilitate modeling. A total of 100 imputed data sets will be generated and results combined for inferential purposes.

Statistical Analysis Plan		Page 12 of 13	
Sponsor	Study		Version
Cochlear Americas	A pivotal, prospective, multi-center, open- label study evaluating the safety and effectiveness of the Cochlear ™ Osia ® 2 System in a pediatric population		1.0

#### 5.6.5.3 Sensitivity Analysis

In the event there is significant evidence of a departure from normality based on a Shapiro-Wilk test at the 0.05 alpha level, a Sign test (a non-parametric alternative) will be employed.

A tipping point analysis for missing data will be performed as a sensitivity analysis. This will impute values for the missing endpoint data, using all possible combinations of the "best" and "worst" observed results for the endpoint (i.e. all missing imputed as "worst", all missing imputed as "best", and all combinations between these extremes).

## 5.7 Poolability Analyses

All investigational sites will follow the requirements of a common protocol and standardized data collection procedures and forms. The primary and secondary endpoints will be presented separately for each site using descriptive statistics. Poolability of the primary endpoints across investigational sites will be evaluated using a regression model with fixed effects for site. For the primary endpoint, analysis will be based on the proportion of subjects experiencing a procedure or device related adverse event and a logistic regression approach. For the secondary endpoint, a linear regression approach will be used. If the p-value for the site effect is 0.15, additional exploratory analyses will be performed to understand any variations in outcomes by site.

## 5.8 Safety Analyses

Adverse events (AEs) will be tabulated with the number of events and subjects with event for each event type and overall. Rates will be reported as the number of subjects who experience at least one event during the analysis interval out of the total number of subjects with follow-up to the beginning of the analysis interval. Serious adverse events (SAEs) will also be tabulated.

All AEs and SAEs will also be summarized by relatedness as described above. Adverse events leading to death or study discontinuation will be provided in listing format.

## 5.9 Subgroup Analyses

Subgroup analysis of the primary and secondary endpoints will be performed for the following subgroups: sex, race (white vs. non-white), age at implantation and etiology of hearing loss. These analyses are intended to demonstrate consistency of results across subgroups.

For the primary safety endpoint, analysis will be based on the proportion of subjects experiencing a procedure or device related adverse event and a logistic regression approach.

Statistical Analysis Plan		Page 13 of 13	
Sponsor	Study		Version
Cochlear Americas	A pivotal, prospective, multi-center, open- label study evaluating the safety and effectiveness of the Cochlear ™ Osia ® 2 System in a pediatric population		1.0

## 5.10 Interim Analyses

No formal interim analyses for the purposes of early stopping for effectiveness or for adaptive sample size re-estimation are planned. Periodic reports on study progress may be reported to regulatory agencies. Regulatory submission is planned to follow the conclusion of the 6 month study visit. Data through 12 months will be considered supplemental.

#### 5.11 Protocol Deviations

Deviations from the procedures outlined in the CIP will be reported by investigational sites on the CRF. Protocol deviations will be summarized for all deviations and by type with event counts and number of subjects with at least one deviation.

## 6 Changes from Planned Analyses

Any changes to planned statistical analyses determined necessary prior to performing the analyses will be documented in an amended Statistical Analysis Plan and approved prior to the analysis when possible. Any other deviations or changes from the planned analyses deemed necessary due to violation of critical underlying statistical assumptions, data characteristics, or missing data will be clearly described in the clinical study report with justification and rationale.

## 7 Subject Listings

Subject listings will be provided for the primary and secondary endpoints.
